3.2 Rationale

FXS is a disorder in which affected individuals display intellectual disability as well as symptoms typical of autism spectrum disorder, due to silencing of the X-linked, *FMR1* gene.

Two previously untested products in FXS were predicted *in silico* to have beneficial activity in FXS and proposed for *in vivo* follow-up in *Fmr1* KO mice, namely ergoloid mesylates (EM) and 5-hydroxytryptophan (5-HTP). Both agents showed an interesting polypharmacological predicted bioactivity spectrum, which is a necessity for complex disorders, such as FXS. The most strongly associated targets after the statistical enrichment were HTR1A, HTR2A, DRD2 and OPRM1 for EM, and ESR1, HTR1A, GRIA1, and GRIK1 for 5-HTP. Both products worked in the majority of tests *in vivo* in the *Fmr1* KO mouse model (see below Section 3.3.1 Preclinical Pharmacology), which led to the hypothesis that their serotonergic action would be additive, whilst the diversity in target and pathway modulation could indeed produce some synergistic effect, which was also confirmed *in vivo*, leading to the alleviation of all FXS phenotypes in the *Fmr1* KO mouse.

3.3 Risk/Benefit

3.3.1 Preclinical Pharmacology

Preclinical *in vivo* data are available for the suggested formulations and their combination. Blinded experiments were conducted to assess the effect of the two treatments and their combination in *Fmr1* KO mice (*Fmr1* gene deletion). Adult male mice were used for all experiments. *Fmr1* knockout mice recapitulate the human phenotype and represent a valuable preclinical model for assessment of putative drug treatments. The *Fmr1* KO carries an insertion in exon 5.⁴ It is a protein null, although *Fmr1* mRNA is still present.⁵ These mice have been backcrossed to the C57/Bl6 or the FVB strains. The *Fmr1* KO2 is a null allele at *Fmr1* generated by deletion of the promoter and first exon of *Fmr1*.⁶ It is both protein and mRNA null. This mutation is the same as is produced by Cre-mediated excision of the loxP sites present in the *Fmr1* KO mice show alterations in the density, size, shape and maturity of dendritic spines, the principle recipients of excitatory inputs from other neurons.¹ Toxicological information on the acute toxicity of 5-HTP in animals are available⁷, as is the corresponding information for EM⁸. The treatment of the mice with 5-HTP, EM was conducted according to the matrix shown below in Table 1.

Group Number	Route	Concentration	Regimen	No. animals
1. WT	-	-	QD	10
2. KO	-	-	QD	10
3. КО 5-НТР	IP	80 mg/kg	QD	10
4. KO EM	РО	4 mg/kg	QD	10
5. KO EM + 5-HTP	PO + IP	2 mg/kg + 40 mg/kg	QD	10

Table 1. Treatment matrix for EM, 5-HTP and the combination in *Fmr1* KO mice.

The behavioural tests performed were for hyperactivity (open field), stereotypy (self-grooming), sociability (three chamber partition test), memory and learning (novel object recognition), anxiety (hyponeophagia), daily living (nest building). Concise definitions follow below.

One-way Analysis of Variance and Dunnett's multiple comparisons against the KO group were performed suggesting that both treatments as well as their combination were significantly different from the KO group (adjusted p-value <0.0001) whilst the actual scoring across tests for both the treatments and their combination was similar to the WT group. Specifically, for all six tests, the treatment combination scoring measurements were found to be very similar to those provided for the WT group. Additional *in vivo* experiments were conducted to assess the effect of SSRIs on 5-HTP + EM treatment, specifically the standard of care SSRI Fluvoxamine was administered (40mg/kg) in another 10 diseased mice. Results confirmed that Fluvoxamine did not alter the effectiveness of 5-HTP + EM treatment (adjusted p-value<0.0001).

Figure 1. Open field WT-V, KO-V, 5-HTP, EM and combination (EM + 5-HTP)

Figure 2. Stereotypy WT-V, KO-V, 5-HTP, EM and combination (EM + 5-HTP)

Figure 3. Sociability WT-V, KO-V, 5-HTP, EM and combination (EM + 5-HTP)

Figure 4. Memory and learning for WT-V, KO-V, 5-HTP, EM and combination (EM + 5-HTP)

Figure 5. Hyponeophagia for WT-V, KO-V, 5-HTP, EM and combination (EM + 5-HTP)

Figure 6. Test of daily living in WT-V, KO-V, 5-HTP, EM and combination (EM + 5-HTP)

3.3.2 Clinical Experience

Ergoloid Mesylates, trade name **Hydergine**, is a mixture of the methanesulfonate salts of three dihydrogenated ergot alkaloids, dihydroergocristine, dihydroergocornine, and alpha- and beta-dihydroergocryptine. Ergot alkaloids are dopamine agonists which activate dopamine receptors (in the basal ganglia and other parts of the brain involved in motor function) and a prolactin inhibitor. Ergot is a strong vasoconstrictor and thus helps to reduce bleeding by narrowing of the blood vessels.

Ergot was perhaps first used in medicine as an oxytocic drug, to promote uterine contraction during childbirth. They have been used for treating migraine headaches since 1883 and also in treating Parkinson's disease, restless leg syndrome, Alzheimer's disease, dementia, hyperprolactinemia and other purposes.⁹

There have been 26 clinical drug trials which investigated the effectiveness of EM in geriatric psychopharmacology, with significant improvement in at least 50% of the studies in the areas of cognitive dysfunctions, mood depression, and the composite scores as measured by subjective clinical behavioral rating scales.¹⁰ Assessments of studies on the effect of EM in dementia have shown strong effects in Vascular Dementia but only a modest efficacy in Alzheimer's Dementia, with a stronger potential on higher dosage,¹¹ as well as a statistically significant improvement on all ten components of the Sandoz Clinical Assessment-Geriatric scale.¹² Olin *et al.*¹³ assessed its overall effects on patients with possible dementia, and showed significant treatment effects. EM was found to be well tolerated in controlled studies of elderly patients with age-related cognitive decline.¹⁴

5-hydroxytryptophan, also known as 5-HTP has a nutraceutical status and has never been approved as a drug for any indication, but as a dietary supplement has been used extensively for several disorders for many years such as in the therapy of depression, fibromyalgia, obesity, insomnia and chronic headache. The starting dose is generally 50 mg, three times a day, which can be doubled after a couple of weeks, if necessary.¹⁵

Despite its relevance to L-tryptophan for which there are safety concerns, 5-HTP has demonstrated a very good safety profile. In humans, 5-HTP has been administered in combination with SSRIs and tricyclic antidepressants,^{16,17} Monoamine oxidase inhibitors (MAOIs)^{18,19,20} and tryptophan.²¹ According to Turner and Blackwell,²² serotonin syndrome has not been reported in humans in association with 5-HTP, either as monotherapy or in combination with other medications. In clinicaltrials.gov (*accessed on 5 Feb 2021*) there are 8 registered clinical studies in phases 2 and 3 involving 5-HTP in one of the arms as a treatment for various indications such as major depressive disorder [NCT04395183], spinal cord injuries [NCT04520178] Crohn's syndrome [NCT03574948] and others.

3.4 Study objectives and endpoints

3.4.1 Study Objectives

In male Fragile X participants aged 18-45 years, inclusive, receiving standard medications:

- To obtain a preliminary assessment of the efficacy of ergoloid mesylates (EM) 1 mg TID, 5hydroxytryptophan (5-HTP) 100 mg TID, and the combination
- To evaluate the safety and tolerability of EM, 5-HTP, and EM + 5-HTP in fragile X syndrome
- To obtain pharmacodynamic (ERP, eye tracking) data on EM, 5-HTP, and EM + 5-HTP

3.4.2 Exploratory Efficacy Outcome Measures

The following instruments will be used to assess the exploratory efficacy endpoints:

- NIH Toolbox Cognitive Battery Modified for Intellectual Disabilities (NIH-TCB)
- Test of Attentional Performance (KiTAP)
- Clinical Global Impression Severity Investigator rated (CGI-S)
- Clinical Global Impression Improvement Investigator rated (CGI-I)
- VAS Rating Scale using participant-specific behavioral anchors
- Aberrant Behavior Checklist (ABC)
- Anxiety, Depression, and Mood Scale (ADAMS)

- Vineland-3 Rating Scale
- Event-Related Potentials (ERP)
- Eye Tracking

3.4.3 Safety and Tolerability Endpoints

The following safety assessments will be conducted during the study.

- Treatment-emergent Adverse events
- Changes in vital signs
- Clinical laboratory evaluations (chemistry, hematology, urinalysis)

4 INVESTIGATIONAL PLAN

4.1 Overall Study Design

This is a single center, Phase 2, single-blind, 4 period study to obtain preliminary assessment of the effects of ergoloid mesylates (EM), 5-hydroxytryptophan (5-HTP), and the combination in participants with Fragile X Syndrome. As schematic display of the study design is shown in Figure 7.

The study will consist of a Screening period of up to 28 days prior to initial study drug administration, followed by four 4-week single-blind treatment periods. The screening and baseline visits may occur at the same time, provided the results of safety labs can be obtained. No washout period will be utilized between treatment periods. A final follow-up phone contact for safety is planned one week after the conclusion of Period 4.

Eligible participants will be started on over-encapsulated EM 1 mg TID during Period 1, then will take EM 1 mg TID and 5-HTP 100 mg TID in Period 2, then 5-HTP 100 mg TID in Period 3, and placebo in Period 4. Throughout all 4 periods, participants will take two identical capsules three times a day. If only taking one over-encapsulated drug, they will take one over-encapsulated placebo pill with the drug at each dose, and when in period 4 they will take two over-encapsulated placebo pills at each dose.

Cognitive and behavioral assessments will be performed during each clinic visit. Safety and tolerability assessments throughout the study will include adverse event monitoring, vital signs, blood chemistry, hematology, and urinalysis.

Figure 7 Study Design Schematic

N=15 participants

4.1.1 Dose Selection

The doses of EM and 5-HTP were chosen as these are standard doses used in clinical management.

EM label for elderly demented patients suggests 1 mg tablets, 3 times a day, according to the product label²³. 5-HTP labels commonly suggest 1-4 tablets totaling 200mg per day, however for depression, most commonly, 150-800 mg daily is taken for 2-6 weeks.²⁴ Given this range, as well as the duration of the study, 100mg TID is suggested for 5-HTP.

Furthermore, when compared to the mouse doses tested in vivo (2 mg/kg for EM and 40 mg/kg for 5-HTP), if these are extrapolated to humans by allometric scaling, i.e. assuming that metabolic rate scales proportionally to body weight raised to the ³/₄ power, the proposed doses of 1 and 100 mg TID for EM and 5-HTP, respectively, are safely lower. Namely the 2 mg/kg mouse dose scales to about 20 mg daily dose for a typical 70 kg male, while for 5-HTP. a 40 mg/kg mouse dose scales to about 400 mg daily dose.²⁵

4.2 Study Duration

The total duration of the study for each participant will be up to 21 weeks, including a maximum of a 4-week screening period, four 4-week single-blind Treatment Periods, and a follow-up call approximately 1 week after last treatment.

5 SELECTION AND WITHDRAWAL OF PARTICIPANTS

5.1 Study Population

Individuals are eligible for the study if they meet all of the inclusion and none of the exclusion criteria. The criteria below will be assessed at the Screening visit which should within 28 days prior to first study drug administration. The Screening and Baseline Visits may be combined if site procedures allow.

5.2 Participant Inclusion Criteria

- 1. Participant is male aged 18 to 45 years, inclusive.
- 2. Participant has Fragile X Syndrome with a molecular genetic confirmation of the full Fragile X Mental Retardation 1 (FMR1) mutation (≥200 CGG repeats).
- 3. Current treatment with no more than 3 prescribed psychotropic medications. Anti-epileptic medications are permitted and are not counted as psychotropic medications if they are used for treatment of seizures. Anti-epileptics for other indications, such as the treatment of mood disorders, count towards the limit of permitted medications.
- 4. Permitted concomitant psychotropic medications must be at a stable dose and dosing regimen for at least 2 weeks prior to Screening and must remain stable during the period between Screening and the commencement of study medication.
- 5. Anti-epileptic medications must be at a stable dose and dosing regimen for 12 weeks prior to Screening and must remain stable during the period between Screening and the commencement of study medication.
- 6. Participants with a history of seizure disorder who are currently receiving treatment with anti-epileptics must have been seizure-free for 3 months preceding screening or must be seizure-free for 3 years if not currently receiving anti-epileptics.
- 7. Behavioral and therapy treatments/interventions must be stable for 4 weeks prior to Screening and must remain stable during the period between Screening and the commencement of study medication, and throughout the study. Minor changes in hours or times of therapy that are not considered clinically significant will not be exclusionary.

Changes in therapies provided through a school program, due to school vacations, are allowed.

- 8. Participant must be willing to practice barrier methods of contraception while on study, if sexually active. Abstinence is also considered a reasonable form of birth control in this study population.
- 9. Participant has a parent, legal authorized guardian or consistent caregiver.
- 10. Participant and caregiver are able to attend the clinic regularly and reliably.
- 11. Participant is able to swallow tablets and capsules.
- 12. For participants who are not their own legal guardian, participant's parent/legal authorized guardian is able to understand and sign an informed consent form to participate in the study.
- 13. If participant is his/her own legal guardian, he/she can understand and sign informed consent to participate in the study.
- 14. If participant is not their own legal guardian, the participant provides assent for participation in the study, if the participant has the cognitive ability to provide assent.

5.3 Participant Exclusion Criteria

The following Exclusions apply to findings during Screening or at Baseline (Day 1):

1. History of, or current cardiovascular, renal, hepatic, respiratory, gastrointestinal, psychiatric, neurologic, cerebrovascular, or other systemic disease that would place the participant at risk or potentially interfere with the interpretation of the safety, tolerability, or efficacy of the study medication.

Common diseases such as mild hypertension, well-controlled type 2 diabetes mellitus (hemoglobin A1C [HgbA1C] <6.5%), etc. are allowed per the investigator's judgment as long as they are stable and controlled by medical therapy that is constant for at least 4 weeks before randomization.

- 2. Clinically significant abnormalities, in the investigator's judgment, in safety laboratory tests, vital signs, or ECG, as measured during Screening.
- 3. History of substance abuse within the past year, according to investigator assessment.
- 4. Use of CYP3A4 inhibitors, beta-blockers, MAO inhibitors or triptans at any time during participation in the study.
- 5. Significant hearing or visual impairment that may affect the participant's ability to complete the test procedures.
- 6. Concurrent major psychiatric condition (e.g., Major Depressive Disorder, Schizophrenia or Bipolar Disorder) as diagnosed by the investigator. Participants with additional diagnosis of Autism Spectrum Disorder or Anxiety Disorder will be allowed.
- 7. Participant has known or suspected human immune deficiency virus-positive status or has diseases such as acquired immunodeficiency disorder, hepatitis C, hepatitis B, or tuberculosis.
- 8. Participant is planning to commence psychotherapy or cognitive behavior therapy (CBT) during the period of the study or had begun psychotherapy or CBT within 4 weeks prior to Screening.
- 9. Participant has participated in another clinical trial within the 30 days preceding Screening.

5.4 Participant Withdrawal

All participants have the right to withdraw from this study at any time. In addition, it is the right of the Investigator to remove participants from the study as a result of adverse reactions, a protocol violation, or non-compliance, or any other reason. Participants must be discontinued for the following reasons:

- Participant withdraws consent or requests discontinuation from the study for any reason;
- Occurrence of a medical condition or circumstance that exposes the participant to substantial risk and/or does not allow the participant to adhere to the requirements of the protocol as determined by the Investigator;
- Any serious adverse event (SAE), clinically significant adverse event, severe laboratory abnormality, concomitant illness, or other medical condition which indicates to the Investigator that continued participation is not in the best interest of the participant;
- Requirement for prohibited concomitant medication;
- Termination of the study by the Sponsor or the regulatory authority.

Should a participant withdraw after administration of EM in Period 1, or should the Investigator decide to withdraw the participant, all efforts will be made to complete and report the protocolstipulated observations up to the time of withdrawal. Week 16 procedures (see Section 10.3.5 and Section 14.1 Schedule of Study Assessments) will be completed at the time of the participant's withdrawal and an explanation provided as to why the participant is withdrawing or being withdrawn from the study.

In a case of participants lost to follow-up, attempts to contact the participant must be made and documented in the participant's medical records.

The Investigator must document the primary reason for discontinuation of a study participant on the appropriate case report form (CRF). If the reason for withdrawal is a clinical AE, monitoring will continue until the AE resolves or the Investigator assesses the AE as chronic and stabilized.

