This is a single-center, Phase 2, single-blind, 4-period sequential study will obtain a preliminary assessment of the effects of ergoloid mesylates (EM) 1 mg TID and 5-hydroxytryptophan (5-HTP) 100 mg TID and the combination compared to a placebo period in participants with Fragile X Syndrome. The study will consist of a Screening period of up to 28 days prior to initial study drug administration, followed by four 4 week single-blind treatment periods. The screening and baseline visits may occur at the same time, provided the results of safety labs can be obtained. A final follow-up visit or phone contact for safety is planned one week after the conclusion of Period 4.

Eligible participants will be started on EM for 4 weeks in Period 1, then will take EM and 5-HTP for 4 weeks in Period 2, then, 5-HTP for 4 weeks in Period 3, then placebo for 4 weeks in Period 4. Study visits will occur at baseline and every 4 weeks at transition times between periods, then at the end of the study.

Brief cognitive and behavioral assessments will be performed during each clinic visit. Safety and tolerability assessments will include adverse event monitoring, vital signs, blood chemistry and hematology, and urinalysis.

	4 Weeks Period 1	4 Weeks Period 2	4 Weeks Period 3	4 Weeks Period 4		
Screen/Enroll ───→	EM	EM + 5-HTP	5-HTP	Placebo		
N=15 participants						
EM=ergoloid mesylates 1 mg TID, 5-HTP = 5-hydroxytryptophan 100 mg TID						
Planned Numbers of Participants						
Enrollment of a total of 15 eligible participants is planned.						
Study Duration						
The total duration of the study for each participant will be up to 21 weeks, including a maximum of 4-week screening						

The total duration of the study for each participant will be up to 21 weeks, including a maximum of 4-week screening period, four 4-week Single-Blind treatment Periods, and a follow-up telephone call approximately 1 week after the last treatment visit.

Study Procedures:

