5.5 Replacement of Participants

Participants who do not meet eligibility criteria at Baseline will not receive any study drug and will be considered screen failures. Participants who withdraw from the study for any reason will not be replaced.

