9.3.5 Early Termination

It is hoped that all participants can be followed through to the conclusion of the study at Period 4/Week 17. However, if an early termination occurs, the Week 16 procedures should be completed at the time of the participant's withdrawal (if possible) and an explanation provided as to why the participant is withdrawing or being withdrawn from the study. Procedures to be completed early termination:

- Collect weight;
- Collect vital signs;
- Draw blood samples for Chemistry and Hematology;
- Collect urine for safety urinalysis;
- Conduct the following cognitive tests:
 - NIH Toolbox Cognitive Battery for Intellectual Disabilities (NIH-TCB)
 - Test of Attentional Performance (KiTAP)
 - Clinical Global Impression Severity Investigator rated (CGI-S)
 - Clinical Global Impression Improvement Investigator rated (CGI-I)
 - Visual Analog Scale (VAS) assessment of participant-specific behavioral anchors
 - Aberrant Behavior Checklist (ABC)
 - Anxiety, Depression, and Mood Scale (ADAMS)
 - Vineland-3 Rating Scale
 - Event-Related Potentials (ERP)
 - Eye Tracking
- Collect study medication and record capsule count remaining in bottle to assess dosing compliance;
- Record any updates to concomitant medication use;
- Assess and record and adverse events; and
- Record final participant disposition.

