10 PLANNED STATISTICAL METHODS

10.1 Sample Size

Given the exploratory nature of this study, a definitive sample size calculation is not possible.

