10.3 Analysis Populations

The primary efficacy population will be the intent to treat (ITT) efficacy population, which will include all randomized participants who received at least one dose of treatment and returned for at least one follow-up visit. The completers population (CP), defined as all randomized participants who completed all treatment periods with no significant protocol violations, will be used to evaluate the robustness of the ITT results.

The Safety population will include all randomized participants who received at least one dose of study treatment.

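### Anyone withdrawn in Periods 1–3 has no placebo value and no rule places his withdrawal assessment, so the placebo and active columns can describe different people

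*Combined protocol and SAP*

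**What the plan says.** - **Order and comparator.** The Synopsis (Study Design) says the regimens are "compared to a placebo period in participants with Fragile X Syndrome". The order is fixed for everyone: EM, EM + 5-HTP, 5-HTP, "then placebo for 4 weeks in Period 4". Section 4.1 repeats it.
- **Size.** "Enrollment of a total of 15 eligible participants is planned" (Synopsis). Section 10.1 adds: "Given the exploratory nature of this study, a definitive sample size calculation is not possible".
- **Stopping.** Section 5.4 describes discontinuation only as leaving the study. Data are to be reported as "observations up to the time of withdrawal". The next sentence, with Section 9.3.5 and the early-termination (ET) column in Section 14.1, requires the Week 16 battery at the time of withdrawal. After that come adverse-event monitoring and a safety call (Synopsis, Study Procedures), but no scheduled efficacy visit. Section 9.3.5 is otherwise only aspirational: "It is hoped that all participants can be followed through to the conclusion of the study at Period 4/Week 17".
- **Replacement.** "Participants who withdraw from the study for any reason will not be replaced" (Section 5.5).
- **Analysis.** Section 10.4 gives descriptive statistics at each time point, with change from the Day 1 baseline for cognitive measures. It has no missing-data rule, no rule for ET values and no within-participant contrast with placebo. Under Section 10.3 the ITT population is dosed participants who came back at least once. The completers population (CP), those who finished every period without significant violations, "will be used to evaluate the robustness of the ITT results".

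**The concern.** The only route to a placebo value runs through all three active periods. A participant who leaves during them is counted in the active columns for the visits he attended and is missing from the placebo column. Some withdrawals will be for adverse events or laboratory findings on an active regimen, so the loss need not be unrelated to treatment. A difference between the placebo column and an earlier column can then reflect who is in each, and its direction cannot be predicted: placebo may be flattered or penalised.

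The ET battery adds a second problem. It is scheduled under Period 4, Week 16, but for someone leaving in Periods 1–3 it is taken on, or just after, an active regimen. Without a rule, a programmer could reasonably put it in the Week 16 column, where active-regimen values would be labelled as placebo.

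**Working it through.** The plan has no sample size or dropout figure to reproduce, so what follows is illustration under stated assumptions.

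**Inputs.** From the documents: N = 15, three active periods before placebo, no replacement. Assumed: dropout d of 5% to 20% per active period; k participants lost before Week 16; a difference δ of 0.5 to 1.0 SD between the mean of those who stay and the mean that those lost would have had.

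**1. How many have a placebo value.** Expected number reaching Period 4 = 15 × (1 − d)³. The chance that at least a given number are missing is a binomial tail with probability 1 − (1 − d)³.

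| d per active period | (1 − d)³ | Expected n reaching placebo | P(≥1 missing) | P(≥3 missing) |
|---|---|---|---|---|
| 5% | 0.857 | 12.9 | 0.901 | 0.363 |
| 10% | 0.729 | 10.9 | 0.991 | 0.816 |
| 15% | 0.614 | 9.2 | 0.999 | 0.965 |
| 20% | 0.512 | 7.7 | >0.999 | 0.995 |

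**2. Shift from selection, ET values excluded.** The mean of all 15 is [(15 − k) × mean(stay) + k × mean(lost)] / 15. Hence mean(stay) − mean(all 15) = (k/15) × δ.

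- k = 1: 0.03 to 0.07 SD
- k = 3: 0.2 × 0.5 = 0.10 SD to 0.2 × 1.0 = 0.20 SD
- k = 5: 0.17 to 0.33 SD

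For the cognitive change scores, δ is a difference in change rather than in level.

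**3. Mixing, ET values entered as Week 16.** Share of the column that is active-regimen data = k/15: 1/15 = 7%, 3/15 = 20%, 5/15 = 33%.

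**4. What the CP comparison can show.**

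- At Week 16 with ET values excluded, the ITT summary already holds only people with a Week 16 value. ITT and CP then differ only by protocol violators, and agreement says nothing about selection.
- At Weeks 4–12, ITT includes later dropouts who attended and CP does not. Take k = 3 who attended Week 4 and left later, with no violators. ITT and CP at Week 4 would differ by (3/15) × δ, or 0.10 to 0.20 SD for the same range of δ. So CP can show selection at those visits, but diluted by k/15 and mixed with the exclusion of violators. Splitting the same data by whether Week 16 was reached shows δ itself.

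**The case against.** The strongest reply has four parts.

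- **The withdrawal battery is planned.** A participant who leaves does supply a final set of values. This is true and useful, but after Periods 1–3 those values are not placebo values, and nothing says where they go.
- **Day 1 is a common reference.** The Synopsis compares post-treatment assessments with a pre-dose baseline that dropout does not affect. That stands and limits the damage. It does not replace the placebo period that the Synopsis names as comparator.
- **The study is exploratory and descriptive.** No test or interval is planned. This limits the severity, but a descriptive table of columns is exactly where a change in who is counted goes unseen.
- **Off-drug Week 16 visits do not recreate a control.** Someone who stops in Period 1 would be assessed about 12 weeks or more after his last capsule. This is correct, which is why such values must be flagged and kept apart.

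A reader might also infer that everyone who tolerates a regimen poorly is lost to placebo, or that the placebo column consists of those who tolerated all three regimens. The documents do not say so. Removal for an adverse reaction rests largely on the investigator's judgement, and someone doing poorly may stay and reach Period 4. Participants may also leave for reasons unrelated to tolerability. That stopping drug means leaving the study is inferred from the wording and from the absence of any other status; no sentence states it.

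**Conclusion.** The point holds for participants withdrawn in Periods 1–3, whatever the reason: they have no placebo value, and the ITT summary by time point can compare different people across columns. The gap in the rule for ET values is separate and equally real.

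The size is unknown because the documents give no dropout rate. With 3 of 15 lost and an assumed δ of 0.5 to 1.0 SD, the Week 16 mean shifts by 0.10 to 0.20 SD. If those three ET sets were entered as Week 16, they would make up 20% of the column. At an assumed 5% dropout per active period, the chance that at least one participant lacks a placebo value is already 90%.

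Two stronger conclusions should not be drawn. First, the CP check is not blind at every visit. It is uninformative about selection at Week 16 if ET values are excluded, but it can reveal selection at Weeks 4–12. Second, smaller numbers at Week 16 would widen any paired interval, but that is lost precision and not selection bias. A paired contrast uses the same people on both sides, so the shift in column make-up does not arise there, although the result then describes only those who stayed.

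**What to change.** Leave the clinical reasons for stopping study drug as they are, and change the following.

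1. **Sections 5.4 and 9.3.5.** Distinguish stopping study drug from withdrawing from the study. Unless consent is withdrawn, participants who stop drug keep the scheduled assessments, at minimum the Week 16 battery. Flag these values as off drug and report them separately, since they are not placebo values. While editing, correct the reference in 5.4 to a Section 10.3.5, which does not exist; early termination is in 9.3.5.
2. **Sections 10.3 and 10.4.** Show Weeks 4, 8 and 12 separately for those who did and did not reach Week 16. Present each active-versus-placebo difference within participants who have both values, with the n for each.
3. **Section 10.4.** Assign ET values to the regimen last taken. For withdrawals in Periods 1–3 they never enter the placebo column.

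**Cost.** Items 2 and 3 use data already collected. Item 1 needs a short amendment and a few visits, already in the schedule, for each participant who stops. The full battery is a burden for this population, and the off-drug values it yields do not recreate placebo data.
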